	
Blood samples will be collected for PD assessment (i.e., APC-PCI) of E-WE thrombin at scheduled time points listed in the Study Events Flow Chart (Section 6) predose and for 24 hours postdose.
 
Dose escalation to the next dose level (i.e., next cohort) will not take place until after the Principal Investigator (PI) has reviewed the safety data and informed the Sponsor of the findings. If any findings in the safety data are of concern, then the Safety Review Committee (SRC) comprised of but not limited to, the Sponsor, medical monitor, and the PI will convene to determine if adequate safety and tolerability from the previous cohorts, including activated partial thromboplastin time (aPTT), has been demonstrated to permit proceeding to the next cohort.
 
For each cohort, 14 days of safety data will be used and reviewed for a dose escalation decision. Data from all subjects in the appropriate cohort will be used and reviewed for a dose escalation decision. aPTT and thrombin time should be in the normal range (unless it is still within <math>\pm 10\%</math> of individual's baseline value taken at check-in) at Day 14 to rule out early cross-reacting antibodies to thrombin/prothrombin. A minimum of 4 subjects in each cohort must complete the study (up to Day 14) before proceeding to the next higher dosing cohort.
 
Subjects dosed on the same day will be dosed with an interval of at least 1 hour between subjects.
 
Subjects (including those who terminate early) will return on Days 14 and 28 for follow-up procedures (coagulation sample collection, thrombin time measurement, and immunogenicity sample collection) and to determine if any AE has occurred since the last study visit. If thrombin time and/or aPTT are found to be elevated beyond normal range (unless it is still within <math>\pm 10\%</math> of individual's baseline value at check-in) at Day 14, both tests will be repeated. If aPTT and/or thrombin time are elevated beyond normal range in the retest, a mixing study will be performed. The mixing study will be performed on Day 14 by mixing the subjects' plasma 1:1 with normal human pooled plasma. aPTT and thrombin time will be evaluated. If the aPTT and/or thrombin time does not correct to normal range, the presence of anti-drug antibodies (ADA) and cross-reacting prothrombin/thrombin antibodies will be presumed, and will be directly assessed before dose escalation decision.
 
Subjects who terminate the study early will be asked to continue aPTT and thrombin time monitoring as scheduled until Day 28.
 
Any subjects for whom aPTT and/or thrombin time did not reach

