### **10.2.4 Follow-up Visits (Day 14 and 28)**

Subjects (including those who terminate early) will return on Days 14 and 28 for follow-up procedures (coagulation sample collection, thrombin time measurement, and immunogenicity sample collection) and to determine if any AE has occurred since the last study visit. If thrombin time and/or aPTT are found to be elevated beyond normal range (unless it is still within  $\pm 10\%$  of individual's baseline value at check-in) at Day 14, both tests will be repeated. If aPTT and/or thrombin time are elevated beyond the normal range in the retest, a mixing study will be performed. The mixing study will be performed on Day 14 by mixing the subjects' plasma 1:1 with normal human pooled plasma and thrombin time evaluated. If the thrombin time does not correct, the presence of ADA and cross-reacting prothrombin/thrombin antibodies will be presumed and will be directly assessed before dose escalation decision. The applicable subject will remain at the CRU until these test results are obtained.

Subjects who terminate the study early will be asked to continue aPTT and thrombin time monitoring as scheduled until Day 28.

Any subjects for whom aPTT and/or thrombin time did not reach  $\pm 10\%$  of the baseline value or within the normal range by Day 14, will return every 7 days ( $\pm 2$  days) until aPTT and thrombin time reach  $\pm 10\%$  of the baseline value or within the normal range and for a FU visit (i.e., follow-up procedures and AE evaluation listed on Day 28 will be repeated) 7 days ( $\pm 2$  days) after it was reached.

Should any subjects withdraw or be withdrawn from the study, all the early termination evaluations should be performed if possible, including samples for PD assessments if applicable.

Immunogenicity samples will be collected at the follow-up visits. The follow-up procedures are listed in the Study Events Flow Chart [Section 6](#).

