### **10.2.5 Scheduled End of Study**

The end of the study is scheduled after completion of the evaluations in the fourth cohort or after dose-limiting clinical safety endpoints have been reached to preclude further increases of dose/cohorts.

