#### **10.4.1.2 Planned Dose Levels**

The planned dose levels are as follows:

Cohort 1: 0.5 mcg/kg E-WE thrombin or matching placebo (IV bolus)

Cohort 2: 1.0 mcg/kg E-WE thrombin or matching placebo (IV bolus)

Cohort 3: 2.0 mcg/kg E-WE thrombin or matching placebo (IV bolus)

Cohort 4: 4.0 mcg/kg E-WE thrombin or matching placebo (IV bolus)

Note: The planned dose levels described above may be revised up or down or a dose level may be repeated based upon data from a previous dose level, however, doses will not exceed 4.0 mcg/kg without a protocol amendment.

For Cohort 1 there will be a sentinel group comprised of 2 subjects dosed at least 28 days before the remaining group of subjects; subjects will be randomized in a 1:1 ratio to active and placebo. The remaining subjects in the cohort will be dosed after evaluation of the sentinel subjects' Day 28 safety data and will be dosed in 2 groups separated by at least 14 days (2 subjects in the first group and 2 subjects in the second group). The placebo will be randomized to either group.

The Cohorts 2, 3, and 4 will be dosed in 2 groups separated by at least 14 days (2 subjects in the first group and 3 subjects in the second group). The placebo will be randomized to either group.

Thrombin time and aPTT at Day 14 will be tested to evaluate whether or not subjects may be generating neutralizing antibodies to thrombin/prothrombin. If the thrombin time and aPTTs are normal, the next cohort may be dosed if the rest of the safety data is deemed acceptable by the PI or SRC, as applicable. Confirmation of safety data from the previous cohorts will include for Cohort 1, 6 subjects (4 active and 2 placebo) and for Cohorts 2, 3, and 4, 5 subjects (4 active and 1 placebo).

If thrombin time and/or aPTT are found to be elevated beyond normal range (unless it is still within  $\pm 10\%$  of individual's baseline value at check-in) at Day 14, both tests will be repeated. If aPTT and/or thrombin time are elevated beyond normal range in the retest, a mixing study will be performed. The mixing study will be performed by mixing the subjects' plasma 1:1 with normal human pooled plasma. aPTT and thrombin time will be evaluated. If the aPTT and/or thrombin time do not correct to normal range, the presence of ADA and cross-reacting prothrombin/thrombin antibodies will be presumed, and will be directly assessed before a dose escalation decision.

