#### **10.4.1.4 Dose Escalation and Stopping Rules**

Dose escalation to the next dose level (i.e., next cohort) will not take place until after the PI has reviewed the safety data. If any findings in the safety data are of concern, then the SRC comprised of but not limited to, the Sponsor, medical monitor, and the PI will convene to determine if adequate safety and tolerability from the previous cohort has been demonstrated to permit proceeding to the next cohort. The SRC review of all pertinent blinded safety/tolerability data must comprise of physical examinations, ECGs, vital signs, clinical laboratory tests [including coagulation], thrombin time, injection site reaction, and AEs available for all subjects who have completed up to Day 14 procedures.

Data from all subjects in the cohort will be used and reviewed for a dose escalation decision and a minimum of 4 subjects must complete the study (up to Day 14) before proceeding to the next higher dosing cohort.

Together they will make one of the following determinations:

1. To continue with the study as planned.
2. To continue with the study and add additional safety evaluations.
3. To continue with the study and repeat a cohort.

4. To continue with the study by adjusting to an intermediate dose between the current dose and the previous lower dose (i.e., add an additional cohort) or to repeat a cohort, if:
  - a. At least 1 subject has a SAE or visit to the emergency room deemed to be possibly study drug related (see [Section 11.1.8.4](#)).
  - b. At least 25% of subjects in a cohort experience a grade  $\geq 2$  AE deemed to be possibly related to the study drug.
5. To stop the study. The study will be terminated if the following number of subjects meet any of the following criteria and the subjects were determined to have received active drug after unblinding:
  - I.  $\geq 1$  subject that receive drug in a cohort experience:
    - a. Life-threatening hypersensitivity reactions (e.g., anaphylaxis, respiratory symptoms, hypotension etc.).
    - b. Any grade thromboembolic event possibly related to the study drug.
    - c. Any grade bleeding possibly related to the study drug.
    - d. Presence of antibodies against human thrombin or prothrombin.
    - e. Presence of ADA.
  - II.  $\geq 2$  subjects that receive drug in a cohort:
    - a. Has a drug possibly or probably related SAE (see [Section 11.1.8.4](#)).
    - b. Experiences a drug related grade  $\geq 3$  toxicity (see [Section 11.1.8.3](#)).

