
Cohorts will be staggered to allow sufficient time for adequate review of safety and tolerability from the prior cohort.

Safety aPTT, PT, and thrombin time data from a cohort will be needed for a dose escalation decision. If aPTT and thrombin time are elevated at Day 14, a mixing study will be performed. If the mixing study does not normalize the aPTT and/or thrombin time, dose escalation will be postponed until ADA data is available. If either ADA assay are confirmed to be positive, the study will be stopped according to the dose escalation and stopping rules outlined above. APC-PCI complex level data will not be needed for a dose escalation decision.

When applicable, a written statement fully documenting the reasons for study termination will be provided to the IRB.

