#### 11.1.7.1 Blood Sampling and Processing for Immunogenicity

Blood samples for immunogenicity assessment (i.e., E-WE thrombin and wild type [WT] thrombin) will be performed as per Study Events Flow Chart (Section 6).

For the determination of E-WE thrombin ADA, blood samples will be collected in 2 blood collection tubes of 4.5 mL each, containing 3.2% sodium citrate, and processed into three plasma aliquots of at least 0.5 mL each.

For the determination of WT thrombin ADA, whole blood samples will be collected in a 5 mL blood collection tube, without anticoagulant, and processed to 3 serum aliquots of 0.5 mL each.

Samples will be shipped to the analytical laboratory for analysis at the end of the study, unless ADA or cross reacting antibodies are suspected from thrombin time elevation at Day 14 or Day 28.

Instruction for blood sampling, collection, processing, and sample shipment will be provided separately.

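### An isolated aPTT prolongation first seen at Day 28 triggers no mandatory repeat, mixing study, early ADA assay or escalation hold

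*Protocol*

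**What the plan says.** Coagulation (including aPTT), thrombin time and immunogenicity samples are collected at both Day 14 and Day 28 (Protocol Sections 6 and 10.2.4; for coagulation also SAP Section 8.4, Table 8.1). Section 10.4.1.2 gives both clotting tests a screening purpose: "Thrombin time and aPTT at Day 14 will be tested to evaluate whether or not subjects may be generating neutralizing antibodies to thrombin/prothrombin".

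The work-up that follows an abnormal value is tied to Day 14. Section 10.2.4 says "The mixing study will be performed on Day 14 by mixing the subjects' plasma 1:1 with normal human pooled plasma and thrombin time evaluated", and continues: "If the thrombin time does not correct, the presence of ADA and cross-reacting prothrombin/thrombin antibodies will be presumed". Section 10.4.1.4 says "If aPTT and thrombin time are elevated at Day 14, a mixing study will be performed", and postpones escalation if that mixing study does not normalize the result.

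Section 11.1.7.1 ships ADA samples at the end of the study "unless ADA or cross reacting antibodies are suspected from thrombin time elevation at Day 14 or Day 28". Section 10.2.5 fixes that end: "The end of the study is scheduled after completion of the evaluations in the fourth cohort", or earlier if dose-limiting safety endpoints are reached.

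On the escalation decision, the Synopsis says "For each cohort, 14 days of safety data will be used and reviewed for a dose escalation decision". Section 10.4.1.4 requires the Safety Review Committee (SRC) to see listed data "available for all subjects who have completed up to Day 14 procedures"; immunogenicity is not on that list.

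**The concern.** The Synopsis presents Day 14 testing as a way to rule out early cross-reacting antibodies. Day 28 is the only scheduled later look, so it is where a slower antibody response would first show. The protocol accepts aPTT alone as a signal at Day 14 and accepts Day 28 as a signal for thrombin time, but no rule covers aPTT alone at Day 28.

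Section 10.4.1.4 stops the study if one subject on active drug has ADA. ADA samples wait until study end by default, so clotting times are the only defined trigger for an earlier result. If that trigger misses a case, the stopping rule has nothing to act on while later subjects are dosed at higher levels.

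**Working it through.** **1. The trigger rules side by side (Protocol)**

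| Place | Visit that triggers | Test that triggers | Read in the mixing study |
|---|---|---|---|
| Synopsis, Study Design | Day 14 | aPTT and/or thrombin time | both |
| Section 6, footnote j | Day 14 | aPTT and/or thrombin time | both |
| Section 10.2.4 | Day 14 | aPTT and/or thrombin time | thrombin time only |
| Section 10.4.1.2 | Day 14 | aPTT and/or thrombin time | both |
| Section 10.4.1.4 (hold) | Day 14 | aPTT *and* thrombin time | both |
| Section 11.1.7.1 (early ADA shipment) | Day 14 or Day 28 | thrombin time only | not applicable |

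The mixing sentence in Section 10.4.1.2 carries no date, but it follows from the Day 14 repeat. No row covers aPTT alone at Day 28. Sections 10.2.4 and 10.4.1.4 also weaken the response to an isolated aPTT prolongation at Day 14 itself.

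**2. How long the ADA result could wait**

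Inputs: sentinels dosed at least 28 days before the rest of Cohort 1; groups within a cohort at least 14 days apart; group sizes 2 + 2 after the sentinels in Cohort 1 and 2 + 3 in Cohorts 2 to 4 (Section 10.3.1); escalation on Day 14 data (Synopsis).

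Assumptions: minimum gaps; decision on the date of the second group's Day 14, with the next cohort dosed that day; all four cohorts run; shipment on the last subject's Day 28.

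Let *t* be days from the sentinel dose, so Day *n* falls on dose date + *n* − 1.

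- Cohort 1 groups at 28 and 42; decision 42 + 13 = 55.
- Cohort 2 groups at 55 and 69; decision 69 + 13 = 82.
- Cohort 3 groups at 82 and 96; decision 96 + 13 = 109.
- Cohort 4 groups at 109 and 123; last Day 28 = 123 + 27 = 150.

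| Group | Dosed | Day 28 | Wait to 150 | Planned subjects dosed on or after that Day 28 |
|---|---|---|---|---|
| Cohort 1 sentinels | 0 | 27 | 123 | 4 + 5 + 5 + 5 = 19 |
| Cohort 1, first | 28 | 55 | 95 | 5 + 5 + 5 = 15 |
| Cohort 1, second | 42 | 69 | 81 | 3 + 5 + 5 = 13 |
| Cohort 2, first | 55 | 82 | 68 | 5 + 5 = 10 |
| Cohort 2, second | 69 | 96 | 54 | 3 + 5 = 8 |
| Cohort 3, first | 82 | 109 | 41 | 5 |
| Cohort 3, second | 96 | 123 | 27 | 3 |
| Cohort 4, first | 109 | 136 | 14 | 0 |
| Cohort 4, second | 123 | 150 | 0 | 0 |

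The last column includes placebo subjects. Assay turnaround is not given and adds to every wait. Slower escalation lengthens the waits; early termination shortens them.

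**3. What a Day 28 hold could reach**

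Cohorts 1 to 3 hold 6 + 5 + 5 = 16 subjects, 12 of them active. Day 28 is due by the earliest decision, or before the rest of Cohort 1 is dosed, for the sentinels and three first groups: 2 + 2 + 2 + 2 = 8. Active among these: 1 + 3 × (1 or 2) = 4 to 7.

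The other 8 (second groups, 2 + 3 + 3) include 12 − 7 = 5 to 12 − 4 = 8 active. Their Day 28 comes 14 days after the decision (69 − 55 = 96 − 82 = 123 − 109 = 14), on the earliest dosing date of the next cohort's second group.

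**The case against.** The strongest reply is that such a finding would not be ignored.

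- Section 10.4.1.4 requires a cohort's aPTT data for the escalation decision without limiting them to Day 14, and the Synopsis names aPTT in the SRC's standard for previous cohorts.
- The investigator or sponsor may order more tests (Sections 11.1 and 11.1.4). Clinically significant values must be evaluated and followed (Section 11.1.8.2). A value failing the clinically significant range forces an investigator flag (SAP Section 8.4).
- The sentinels' Day 28 data must be evaluated before the rest of Cohort 1 is dosed.
- Section 11.1.7.1 concerns shipping and need not list every ground for early release.
- Footnote l in Section 6 has Day 28 samples tested for ADA eventually.

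All of this stands as mitigation. It brings aPTT into the review, but none of it requires a repeat, a mixing study or an early ADA assay. The protocol chose a fixed rule over judgement at Day 14; the same reasoning applies at Day 28.

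Other points stand as limits. The 123-day figure belongs to a pair with only one active subject and a required Day 28 review. Cohort 4 has no planned higher dose after it. Six of the eight subjects a hold could reach have Day 28 on the decision date itself, so the hold needs same-day results or a short delay. Harm requires a chain: acceptable values at Day 14, aPTT alone prolonged at Day 28, an ADA-positive subject on active drug, and no discretionary action.

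Section 10.4.5 implies that participants generally are followed until values recover, whereas the weekly-return rule elsewhere says by Day 14. That passage can also be read as describing the existing rule, so little weight rests on it.

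**Conclusion.** The gap is real. For completing subjects, no rule requires a response to an isolated aPTT prolongation first seen at Day 28, and Sections 10.2.4 and 10.4.1.4 disagree with the *and/or* rule stated elsewhere even at Day 14. If the pattern occurs in Cohorts 1 to 3 and nobody acts on discretion, the ADA sample waits 27 to 123 days for shipment under the minimum-spacing assumptions, with 3 to 19 planned subjects still to be dosed. How often this would happen cannot be estimated from the documents. Because discretionary routes exist, this is a recommended correction and does not invalidate the design. Confidence in the reading is high.

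**What to change.** 1. In Protocol Section 11.1.7.1, release ADA samples early for aPTT and/or thrombin time elevation at Day 14 or Day 28.
2. In the Synopsis, Section 6 footnote j, and Sections 10.2.4, 10.4.1.2 and 10.4.1.4, trigger the repeat and mixing study on aPTT and/or thrombin time elevation at either visit, and do the mixing study at the visit concerned. In Section 10.2.4, read aPTT as well as thrombin time.
3. Extend the weekly return to a Day 28 prolongation wherever it is stated: Synopsis, Section 6 footnotes d and j, Sections 10.1.1, 10.2.4 and 10.4.1.2, Table 3 in Section 11.4, and SAP Section 3.
4. Apply the existing hold in Section 10.4.1.4 to any Day 28 prolongation known at the escalation decision or the sentinel review.

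For the second groups in Cohorts 1 to 3, item 4 comes too late; their gain is an earlier ADA result feeding the stopping rule. Covering the next cohort's second group would need the hold to apply to that dosing date as well.

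The cost is wording. Extra blood for an affected subject, using Table 3 volumes and *k* weekly visits, is 3.5 (repeat) + 3.5*k* + (3.5 + 9 + 5) (closing visit) = 21 + 3.5*k* mL: 24.5 mL at *k* = 1, 35 mL at *k* = 4 and 49 mL at *k* = 8. That stays within Table 3's 50 mL allowance up to *k* = 8; the same table's cap of about 500 mL for continued clotting-time sampling is far looser. The mixing-study volume is not stated and is assumed to come from the repeat tube. The downside is occasional extra tests and visits for chance findings, and possibly a short delay to escalation.

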### **10.2.5 Scheduled End of Study**

The end of the study is scheduled after completion of the evaluations in the fourth cohort or after dose-limiting clinical safety endpoints have been reached to preclude further increases of dose/cohorts.

## **10.3 Selection of Study Population**

### **10.3.1 Number of Subjects**

The study is planned to enroll up to 21 subjects in 4 cohorts [i.e., dose levels] with 6 subjects in Cohort 1 [4 subjects randomized to receive the active drug and 2 subjects to receive the placebo] and 5 subjects in Cohorts 2, 3, and 4 [4 subjects randomized to receive the active drug and 1 subject to receive the placebo]. In each cohort, an attempt will be made to have at least 30% of the subjects be of a race/ethnicity minority group. An attempt will be made to include at least 2 females in each cohort.

Cohort 1 will contain a sentinel group of 2 subjects (1 placebo and 1 active). The sentinel group will be dosed at least 28 days before the remaining subjects in Cohort 1. The remaining subjects in the cohort will be dosed after evaluation of the sentinel subjects' Day 28 safety data and will be dosed in 2 groups separated by at least 14 days (2 subjects in the first group and 2 subjects in the second group). The placebo will be randomized to either group.

The Cohorts 2, 3, and 4 will be dosed in 2 groups separated by at least 14 days (2 subjects in the first group and 3 subjects in the second group). The placebo will be randomized to either group.

Additional subjects (up to 6 subjects per cohort) may be enrolled if it is deemed appropriate by the PI and the Sponsor to repeat a dose level or to study an intermediate dose level (lower than those planned) in a new cohort of subjects.

### **10.3.2 Inclusion Criteria**

Subjects must fulfill all of the following inclusion criteria to be eligible for participation in the study:

1. Healthy, adult, male and/or female (females of non-childbearing potential only), 18 to 55 years of age, inclusive, at screening.
2. Continuous non-smoker, who has not used nicotine-containing products for at least 3 months prior to dosing, based on subject self-reporting.

3. Body mass index (BMI)  $\geq 18$  and  $< 29$  (kg/m^2) at screening and weight between 50 and 125 kg (inclusive) at screening.
4. Medically healthy with no clinically significant medical history, physical examination, laboratory profiles, vital signs or ECGs, as deemed by the PI or designee.
5. A female must be of non-childbearing potential and must have undergone one of the following sterilization procedures at least 6 months prior to dosing:
  - a. hysteroscopic sterilization;
  - b. bilateral tubal ligation or bilateral salpingectomy;
  - c. hysterectomy;
  - d. bilateral oophorectomy.or be postmenopausal with amenorrhea for at least 1 year prior to dosing and follicle-stimulating hormone (FSH) serum levels consistent with postmenopausal status.
6. A non-vasectomized, male subject must agree to use a condom with spermicide or abstain from sexual intercourse during the study until 90 days beyond the dose of study drug. (No restrictions are required for a vasectomized male provided his vasectomy has been performed 4 months or more prior to dosing of study drug. A male who has been vasectomized less than 4 months prior to dosing must follow the same restrictions as a non-vasectomized male).
7. If male, must agree to not donate sperm from dosing until 90 days after dosing.
8. Understands the study procedures in the informed consent form (ICF), and be willing and able to comply with the protocol.

